## 3.2 Study Design

This is a multinational phase 3, randomized, double-blind, placebo-controlled efficacy and safety study of enzalutamide plus ADT versus placebo plus ADT in patients with mHSPC. After the double-blind period has completed, eligible patients were allowed to received open label enzalutamide in an open label extension period.

Approximately 1100 subjects were randomized centrally 1:1, and the randomization was stratified by volume of disease (low versus high) and prior docetaxel therapy for prostate cancer (no prior docetaxel, 1-5 cycles, 6 cycles). High volume of disease is defined as metastases involving the viscera or, in the absence of visceral lesions, there must be 4 or more bone lesions, at least 1 of which must be in a bony structure beyond the vertebral column and pelvic bone. Prior docetaxel therapy is defined as 1 or more cycles of docetaxel but no more than 6 cycles.

In this study, patients received 4 capsules of enzalutamide (40 mg each) or placebo per day orally in the double-blind period. After the double-blind period has completed, eligible patients received 4 capsules of enzalutamide (40 mg each) in the open label extension period. As long as the patient is tolerating the study drug, the treatment should be continued until radiographic disease progression (rPD) or starting an investigational agent or new therapy for treatment of prostate cancer. Patients who discontinue study drug without radiographic progression will continue to follow the radiographic assessment schedule until radiographic progression event or until the target number of deaths is reached for the final analysis of OS.

The following assessments of prostate cancer status will be collected during OLE: soft tissue disease on CT scan or on MRI, bone disease on radionuclide bone scans, survival status, EQ-5D-5L, QLQ-PR25, FACT-P for QoL and BPI-SF for pain symptom assessment. Throughout the study, safety and tolerability were assessed by the recording of adverse events (AE), vital signs, physical examinations, 12-lead electrocardiograms (ECG), and safety laboratory evaluations (including PSA).

Patients will have a safety follow-up visit 30 days after their last dose of study drug or prior to initiation of new antineoplastic therapy for prostate cancer, whichever occurs first. All

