#### 6.1 Overall Survival

OS is defined as the time from randomization to death from any cause. All deaths on or before the data cut-off will be included.

For patients who are alive at the time of the cut-off date, OS time will be censored on the last date the patient is known to be alive or the cut-off date, whichever occurs first. The date the patient is last known alive by the cut-off date will be derived as follows:

- for patients on treatment by the cut-off date (i.e., patients who did not discontinue from treatment), the date last known alive will be the cut-off date.
- for patients who withdraw consent by the cut-off date, the date last known alive is the date of consent withdrawal.
- for patients lost to follow up, the date last known alive depends on the period the patient was lost to follow-up. It will be as follows:

Period lost to follow-up	The date last known alive		
Since randomization (i.e. without	The date of randomization		
further post-randomization visit)			
During treatment period	The last assessment/visit date or the date of the last		
	dose of study drug, whichever occurs later		
Safety follow-up period	The date of the last dose of study drug or the last		
	treatment visit date collected on the End of Treatment		
	Case Report Form (CRF) page, whichever occurs last.		
Long-term follow-up period	The last visit/contact date (collected either on the		
	30 Day Follow-Up Status CRF page, or the Patient		
	Status - Survival CRF page or the Long-Term Follow-		
	Up Status CRF page).		

• for other patients (i.e., not on treatment, not withdrawn and not lost to follow-up) who are alive by the cut-off date, the date last known alive is the date of last visit (collected either on the Patient Status - Survival CRF page or the Long-Term Follow-Up Status CRF page) or the date of randomization, whichever occurs last.

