#### 7.12.3 Visit Windows

Visit windows are allowed for certain visits per the schedule of assessments. Patient data will not be excluded from analyses due to the patient's failure to comply with the visit schedule.

For summary tables reporting results by visit, analyses of efficacy and safety variables will be performed according to the analysis visit windows described in the following Table 4.

In the case of multiple observations in the same analysis visit window, the observation which is closest to the target date will be used. If the observations have the same distance to the target visit day, the latest one will be used (using date, and time if available). Should there be two assessments documented at the same time due to the repetition of analysis of the same sample, the one reported as scheduled will be used.

Scheduled Visit	Analysis Visit*			
Week 1 (Day 1)	Baseline**			
Week 5 (Day 29)	Week 5			
Week 13 (Day 85)	Week 13			
For the next visits during the treatment period:				
Week X = Week (i*12+13), (i=1,2,3,) Week X target day = i*12*7 + 85, (i=1,2,3,) Week X (Wk X target day - 41 days; Wk X target day + 42 days)				
However, for the (last) visit during the treatment period, i.e. the last dose day of study drug is recorded, the upper boundary of the analysis visit window is 5 days after the last dose day, e.g.				
Week X = Week (i*12+13), (i=0,1,2,3,) Week X target day = i*12*7 + 85, (i=0,1,2,3,) Week X (Wk X target day - 41 days; last dose day + 5 days)				
last dose day + 30 days	30 Day Safety F-up (after last dose or prior to new therapy)			
	Scheduled Visit Week 1 (Day 1) Week 5 (Day 29) Week 13 (Day 85) visits during the treatment = Week (i*12+13), (i=1,2) get day = i*12*7 + 85, (i=1) t day - 41 days; Wk X tar the treatment period, i.e. recorded, visit visit window is 5 day Week (i*12+13), (i=0,1, et day = i*12*7 + 85, (i=0) get day - 41 days; last do last dose day + 30 days			

Table 4Analysis Visit Windows

Visit Day Interval	Scheduled Visit	Analysis Visit*		
Patients who end treatment before the data analysis cut-off date and have long-term (LT) follow-up				
visits,				
have visits every 12 weeks after last dose day:				
LT F-up $j = j*12$ weeks visit after last dose day, $(j=1,2,3,)$				
LT F-up j target day = $j*12*7 + last dose day, (j=1,2,3,)$				
LT F-up j ( $j*12*7 + last dose day - 41$ ; $j*12*7 + last dose day + 42$ )				

F-up: follow-up

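### SAP 6.1 censors a living subject who has recently stopped treatment at randomization if neither the Survival page nor the Long-Term Follow-Up page has a dated entry by the cut-off

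*SAP*

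**What the plan says.** SAP 6.1 opens with a general principle for subjects alive at the cut-off: "OS time will be censored on the last date the patient is known to be alive or the cut-off date, whichever occurs first". It then derives the last-alive date by category.

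- **Still on treatment:** "the date last known alive will be the cut-off date".
- **Lost during safety follow-up:** the later of last dose and the last treatment visit on the End of Treatment page (the entry begins "The date of the last dose of study drug or the last").
- **Lost during long-term follow-up:** the last visit or contact on any of three pages, one of which is the 30 Day Follow-Up Status page.
- **Everyone else**, described as "for other patients (i.e., not on treatment, not withdrawn and not lost to follow-up) who are alive by the cut-off date". For this group only two case report form pages may supply a visit date, the first being the survival status form. The provision names the second page and the floor in these words: "or the Long-Term Follow-Up Status CRF page) or the date of randomization, whichever occurs last".

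On timing, SAP 3.2 states: "Patients will have a safety follow-up visit 30 days after their last dose of study drug". SAP 7.12.3 says that subjects in long-term follow-up "have visits every 12 weeks after last dose day". SAP 7.1 restricts reporting to data on or before the cut-off. SAP 7.12 counts a duration as the difference in dates plus one day.

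**The concern.** The last category omits three sources that show a man was alive: last dose, the End of Treatment page and the 30 Day Follow-Up Status page. If he stopped drug shortly before the cut-off, and neither named page has an entry yet, the only date left is randomization. His known survival disappears from the analysis.

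Time is removed only from living subjects, and the trigger is recent discontinuation, which is unlikely to be unrelated to prognosis. Deaths are counted as before over a smaller time at risk, so estimated hazards rise and Kaplan-Meier survival falls. If recent stoppers are unevenly spread between arms, the hazard ratio and log-rank test shift too. OS carries formal type I error (2-sided 0.04), so its censoring rule should be exact.

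Other outputs are touched:

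- Median follow-up (SAP 7.4.1) reverses the censoring flag, so each affected subject becomes an event at day 1.
- In the rank-preserving structural failure time analysis, an affected crossover subject would have an OS time ending before his open-label exposure began.
- SAP 6.2 censors time to new antineoplastic therapy at the last visit with no page restriction. The same man could have 1 day of OS and years on that endpoint.

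**Working it through.** **1. The plan's event count.** Inputs from SAP 4 and 7.4.1: HR 0.73, 80% power, 2-sided 0.04, 1:1.

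- Schoenfeld: 4(2.054 + 0.842)²/(ln 0.73)² = 33.53/0.0990 = 339.
- Freedman: (2.054 + 0.842)² × (1.73/0.27)² = 8.383 × 41.06, giving 345.
- The stated 342 lies between them. Power at 342 deaths is Φ(√342 × 0.3147/2 − 2.054) = Φ(0.856) = 80.4%.

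The count is sound and does not depend on the censoring rule.

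**2. The rule applied.** Take a man whose last dose was 60 days before the cut-off and who has attended his 30-day visit.

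- His first long-term visit has its target at day 84, so he may have no entry on either named page. Randomization is then the later of the permitted dates, and OS = 0 + 1 = 1 day.
- Had he been lost during safety follow-up, he would keep time to last dose or the End of Treatment visit.
- Had he still been on drug, he would keep time to the cut-off.

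The subject still in the study keeps the least.

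**3. Size, by simulation.** From the documents: 1100 subjects, 1:1, control median OS 40 months, HR 0.73, cut-off at the 342nd death. Assumptions not in the documents:

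- 24-month uniform accrual;
- exponential OS and time on treatment, independent of each other, with no crossover;
- no entry on either page until 84 (or 30) days after last dose, and no survival contact at the cut-off;
- other survivors followed to the cut-off.

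Treatment medians of 20/30 months borrow the planning medians for radiographic progression-free survival (Protocol 7.1); 12/36 and 30/30 are alternatives. There were 1500 trials per row. The corrected rule censors affected subjects at last dose.

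| Treatment medians, placebo/enzalutamide | Gap (days) | Subjects reset, placebo + enzalutamide | OS follow-up lost | HR, corrected → SAP rule | Power, corrected → SAP rule |
|---|---|---|---|---|---|
| 20/30 | 84 | 15.9 + 15.2 | 3.0% | 0.7337 → 0.7322 | 81.8 → 82.1% |
| 12/36 | 84 | 16.1 + 13.7 | 2.8% | 0.7335 → 0.7310 | 81.9 → 82.5% |
| 30/30 | 84 | 13.6 + 15.2 | 2.8% | 0.7339 → 0.7351 | 81.8 → 81.1% |
| 20/30 | 30 | 5.5 + 5.4 | 1.1% | 0.7339 → 0.7335 | 81.8 → 81.5% |
| 12/36 | 30 | 5.5 + 4.8 | 1.0% | 0.7339 → 0.7332 | 81.8 → 82.2% |
| 30/30 | 30 | 4.8 + 5.4 | 1.0% | 0.7339 → 0.7344 | 81.8 → 81.7% |

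With 1100 − 342 = 758 survivors, 30 resets are 30/758 = 4.0% of them.

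With no treatment effect and an 84-day gap, the mean HR moves from 1.0049 to 0.9988 (20/30) or from 1.0044 to 0.9949 (12/36). The larger shift, 0.0095, is under a tenth of the standard error of the log HR (2/√342 = 0.108). Rejection goes from 4.2% to 4.5% and from 4.1% to 4.5%; the simulation error of each rate is √(0.04 × 0.96/1500) = 0.5 points.

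**4. Kaplan-Meier curves.** Losing 3% of follow-up with the same deaths raises the hazard by about 1/0.97 = 1.031.

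- Placebo at 36 months: exp(−0.6238) = 53.6% becomes exp(−0.6431) = 52.6%.
- Enzalutamide (median 55): exp(−0.4537) = 63.5% becomes exp(−0.4677) = 62.6%.

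Each arm falls by about 1 point.

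**The case against.** The strongest reply is that the group may be nearly empty. Randomization is only a floor; one dated entry on either page removes the problem. The protocol and SAP make long-term follow-up mandatory, let it be done by telephone, and say that extra contacts may be requested. A survival contact for everyone at the cut-off would leave nobody affected. The first long-term analysis window in SAP 7.12.3 opens at 84 − 41 = 43 days after last dose, so day 84 is not necessarily the earliest entry. The main study SAP, to which this one defers for definitions, is not among the documents.

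Much of this stands: it limits the size and makes it uncertain. It does not rescue the text. No survival contact at the cut-off is required. The timing of the Survival page is undefined, and in the lost-to-follow-up table that page appears only under the long-term period. SAP 6 presents itself as giving the modified derivations.

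Three stronger readings are tempting but not supported.

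- **That every recent stopper is reset.** Only those with no entry on either page are.
- **That power falls materially.** Resetting 2% of placebo and 4% of enzalutamide survivors moves the HR from 0.720 to 0.733 and power from 80% to about 75%; 3% against 6% gives 0.722 to 0.742 and about 73%. Those splits are imposed. Under constant discontinuation of 10 to 50% a year, the reset share stays below 5% of survivors, so 6% is not reached. A split of 2% against 4% needs about 10% a year stopping on placebo and 30% on enzalutamide, opposite in direction to the planning medians of 20 and 30 months.
- **That the arm with more subjects still on treatment is penalised.** Those subjects are censored at the cut-off and untouched. Recent stoppers matter, and the table shows the HR moving either way.

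**Conclusion.** Wrong as written, with low expected impact on the OS conclusion. The derivation contradicts the section's own principle and its handling of subjects lost during safety follow-up. This is a stated rule that gives a wrong date, not merely an omitted detail.

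Under the assumptions above, an 84-day gap resets about 30 subjects and loses about 3% of OS follow-up; a 30-day gap resets about 11 and loses about 1%. Kaplan-Meier estimates and median follow-up are slightly distorted. At the target effect the HR moves by about 0.003 or less, in a direction set by which arm has more recent stoppers, and power by about 1 point. These figures are illustrations, not trial results. They do not model crossover to open-label enzalutamide, and they fall to zero if every subject has a survival contact at the cut-off.

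**What to change.** In SAP 6.1, for living subjects who are off treatment, not withdrawn and not lost, define the last-alive date as the latest documented date of being alive on or before the cut-off. Eligible sources are last dose, any visit or assessment, and the End of Treatment, 30 Day Follow-Up Status, Survival and Long-Term Follow-Up Status pages. Use randomization only if no later date exists. It would also help to state when the Survival page is completed and whether all subjects are contacted at the cut-off.

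The cost is one sentence and one change to the derivation program. The dates are already collected, the 342-death requirement is unchanged, and nothing in the conduct of the trial is affected.

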#### 6.2 Time to Initiation of a New Antineoplastic Therapy

The initiation of a new antineoplastic therapy is based on the information collected in the (new) prostate cancer therapy CRF pages about all antineoplastic therapies, including cytotoxic and hormone therapies, initiated for prostate cancer subsequent to the study drug.

In patients with a new antineoplastic therapy initiated for prostate cancer, time to initiation of a new antineoplastic therapy (i.e., time to new antineoplastic therapy) is defined as the time interval from randomization to the date of first dose administration of the first antineoplastic therapy.

In patients with no new antineoplastic therapy initiated for prostate cancer, time to start of new antineoplastic therapy will be censored on the last visit date or the date of randomization, whichever occurs last.

#### 6.3 Treatment Emergent Adverse Event (TEAE)

A TEAE is defined as an AE that occurs or worsen at any time during the treatment emergent period. The treatment emergent period is time interval encompassing the double-blind treatment emergent period and the OLE treatment emergent period.

The double-blind treatment emergent period is defined as the time interval from the first double-blind study drug intake up to 30 days after the date of the last dose of double-blind study drug, study discontinuation, the start of new antineoplastic therapy, or the first dose of OLE treatment, whichever occurs first.

If AE start date is the same date as the study start, then it will be considered as a TEAE if the box 'Onset after first dose of study' is ticked in the Electronic case report form(eCRF). If a patient experiences an event both during the pre-investigational period and during the investigational period, the event will be considered as TEAE only if it has worsened in severity (i.e. it is reported with a new start date).

The OLE treatment emergent period is defined as the time interval from the OLE study drug intake up to 30 days after the date of the last dose of OLE study drug, study discontinuation, or the start of new antineoplastic therapy, whichever occurs first.

AE with both a missing start and stop dates, and AEs with a missing start date but has a known stop date which is on or after the first dose of study drug will be considered treatment-emergent.

For each treatment group, the treatment emergent period is as follows;

- Enzalutamide group: from the first DBT study drug intake up to 30 days after the date of the last dose of study drug, study discontinuation, or the start of new antineoplastic therapy, whichever occurs first.
- Placebo group: from the first DBT study drug intake up to 30 days after the date of the last dose of placebo, start of open-label enzalutamide, study discontinuation, or the start of new antineoplastic therapy, whichever occurs first.
- Placebo crossover group: from the first OLE study drug intake up to 30 days after the date of the last dose of OLE study drug, study discontinuation, or the start of new antineoplastic therapy, whichever occurs first.

AEs will be coded to System Organ Class (SOC) and preferred term using MedDRA v23.0 and severity graded using National Cancer Institute's Common Terminology Criteria version 4.03 (NCI-CTCAE v4.03) for AEs.

## 7 STATISTICAL METHODOLOGY

## 7.1 General Considerations

For continuous variables, descriptive statistics will include the number of patients (n), mean, standard deviation, median, minimum and maximum. When needed, the use of other percentiles (e.g. 10%, 25%, 75% and 90%) will be mentioned in the relevant section.

Frequencies and percentages will be displayed for categorical data. Unless otherwise specified, percentages by categories will be based on the number of patients with no missing data, i.e. will add up to 100%.

All listings will be produced by site and patient id numbers in ascending order.

Disposition, demographics, other baseline characteristics and efficacy data will be summarized based on the ITT population, unless stated otherwise. Safety analysis summary and other summaries based on SAF are presented by actual treatment received, unless stated otherwise.

All statistical comparisons will be made using two sided tests. All null hypotheses will be of no treatment difference.

All data processing, summarization, and analyses will be performed using SAS® Version 9.4 or higher on Unix. Specifications for table, figures, and data listing formats can be found in the TLF specifications for this study.

For the definition of subgroups of interest, please refer to section 7.9.

A data analysis cut-off date for the database will be used. All data from visits or assessments done on or prior to the cut-off date will be reported.

#### 7.2 Study Population

#### 7.2.1 Disposition of Subjects

The following subject data will be presented for Enzalutamide, Placebo and Placebo crossover group:

- Number of patients randomized in DBP, received treatment in DBP, with ICF for OLE and received treatment in OLE (All Randomized Subjects).
- Treatment disposition in DBP (All Randomized Subjects) and OLE (All subjects on Enzalutamide)
- Number of patients who took study drug, patients who did not take study drug in DBP and OLE
- Number and percentage of patients by study visits completed in DBP and OLE, based on the SAF
- Number and percentage of patients who discontinued from the treatment in DBP and OLE by primary reason for discontinuation
- Number and percentage of patients who discontinued from the 30 day safety followup in DBP and OLE by primary reason for discontinuation
- Number and percentage of patients who discontinued from the long term follow-up in DBP, OLE and overall by primary reason for discontinuation
- Number of patients with protocol deviations in DBP and OLE
- Number of OLE patients by site and country

Treatment disposition, 30 day follow-up disposition, and long term follow-up disposition, randomization information will be listed. The protocol deviations, as well as the description of protocol deviation criteria will also be listed.

#### 7.2.2 **Protocol Deviations**

Protocol deviations as defined in the study protocol (Section 8.1.6 Protocol Deviations) will be assessed for all randomized patients.

The protocol deviation criteria will be uniquely identified in the summary table by study period (DBP and OLE) and in listing. The unique identifiers will be as follows:

- PD1 Entered into the study even though they did not satisfy entry criteria,
- PD2 Developed withdrawal criteria during the study and was not withdrawn,
- PD3 Received wrong treatment or incorrect dose,
- PD4 Received excluded concomitant treatment.

Patients deviating from a criterion more than once will be counted once for the corresponding criterion. Any patients who have more than one protocol deviation will be counted once in the overall summary.

The number and percentage of patients meeting any criteria will be summarized for each criterion and in total, for Enzalutamide, Placebo and Placebo crossover group, as well as by country, study site and by study period. Inclusion and exclusion criteria will be summarized for each criterion for Placebo crossover group.

A data listing will be provided by site and patient, where each protocol deviation will be indicated according to the period in which it had occurred.

#### 7.2.3 Demographic and Other Baseline Characteristics

Demographic and baseline characteristics (at the time of randomization) will be summarized for Placebo crossover group on the ITT.

Descriptive statistics for age and height at study entry will be presented along with frequency tabulations for age group (< 65, 65- <75 and >= 75; and EudraCT age groups), ethnicity, race, Geographic region, at study entry. The weight, body mass index (BMI), ECOG status, PSA, and ALP at baseline will also be presented by descriptive statistics. The 10%, 25%, 75% and 90% percentiles will be provided for PSA, and ALP at baseline.

Disease History, Results of Metastasis at screening, Prostate Cancer Treatment History (Radiation and Procedures) and Non-Prostate Cancer Related Medical History will be summarized for Placebo cross-over group on the ITT.

Number and percentage of patients randomized in each country and site will also be summarized.

